12.4.5 Summary of Abnormalities in Worst Post-Baseline in Liver Function Tests

Target population	:	Safety Analysis Set
Analysis Items	:	Liver Function Tests
Content of analysis	:	
 • The number and percentages of patients by groups, analysis items and category. • Category is as follow: ALT, AST, ALT or AST: <= ULN, > ULN & <= 3xULN, > 3xULN & <= 5xULN, > 5xULN & <= 10xULN, > 10xULN & <= 20xULN, > 20xULN, Missing Total Bilirubin: <=ULN, > ULN & <= 1.5xULN, > 1.5xULN <= 2xULN, > 2xULN <= 3xULN, > 3xULN <= 5xULN, > 5xULN, Missing Alkaline Phosphatase: <=ULN, >ULN & <=1.5xULN, >1.5xULN, Missing AST or ALT and Concurrent Total Bilirubin: (AST > 3xULN or ALT >3xULN) and Total Bilirubin > 2xULN
Definition	:	• The denominator of proportions is the target population by groups.

12.4.6 Mean (+/- SEM) of Laboratory Parameters for Liver Function Tests/eGFR/Potassium by Visit

Target population	:	Safety Analysis Set
Analysis Items	:	Liver Function Tests, eGFR, Potassium (Refer to Appendix 2)
Group	:	Placebo, Zilebesiran 300 mg, Zilebesiran 600 mg
Time of analysis	:	Refer to section 2.8.1

Content of analysis	:	
 • Trend diagram of Mean \pm SEM of measurement value will be presented graphically by groups, analysis visit in 6-Month DB period and Safety/PD Follow-up
---------------------	---	--

12.4.7 eDISH Plot of Post-baseline Peak ALT or AST versus Total Bilirubin/ALT versus Total Bilirubin/AST versus Total Bilirubin, Per Patient

Target population	:	Safety Analysis Set
Analysis Items	:	AST, ALT, Total Bilirubin
Group	:	Placebo, Zilebesiran 300 mg, Zilebesiran 600 mg
Time of analysis	:	Refer to section 2.8.1
Content of analysis	:	
 • eDISH plot will be presented graphically by groups, patients. • The target of the analysis are patients who have post-baseline data
Definition	:	
 • Peak value is defined as the highest data of analysis item.

12.4.8 Spaghetti Plot for Liver Function Tests during 6-Month DB Period

Target population	:	Safety Analysis Set
Analysis Items	:	Liver Function Tests (Refer to Appendix 2)
Group	:	Placebo, Zilebesiran 300 mg, Zilebesiran 600 mg
Time of analysis	:	Refer to section 2.8.1
Content of analysis	:	
 • Spaghetti Plot for measurement value and percent change from baseline of each analysis item by group, analysis visit in 6-Month DB period

12.4.9 Spaghetti plot for Potassium for Patients with Post Baseline >5.5 (mmol/L) during 6-Month DB Period

Target population	:	Safety Analysis Set
Analysis Items	:	Potassium (Refer to Appendix 2)
Group	:	Placebo, Zilebesiran 300 mg, Zilebesiran 600 mg
Time of analysis	:	Refer to section 2.8.1
Content of analysis	:	
 • Spaghetti Plot for measurement value and percent change from baseline of analysis item by group, analysis visit in 6-Month DB period

12.5 Prior and Concomitant Medication, Prior and Concomitant Anti-hypertensive medication

12.5.1 Summary of Prior and Concomitant Medication, Prior and Concomitant Anti-hypertensive

medication

Target population	:	Safety Analysis Set
Group	:	Placebo, Zilebesiran 300 mg, Zilebesiran 600 mg, Total zilebesiran, Overall Total
Analysis Items	:	Prior medication, Concomitant medication, Prior Anti-hypertensive medication, Concomitant Anti-hypertensive medication.
Content of analysis	:	
 • The number and percentages of patients with at least one prior medication will be summarized by groups. • For prior medications, the number and percentage of patients who took each medicine will be summarized by High level term and Preferred Term. • Concomitant medication, Prior Anti-hypertensive medication, Concomitant Anti-hypertensive medication will be summarized as well as prior medication.
Definitions	:	
 • The denominator is the target population by groups.

13. Listings to create

- 13.1 Listing of Screened Patient
- 13.2 Listing of Randomization
- 13.3 Listing of Patient Disposition
- 13.4 Listing of Protocol Deviations
- 13.5 Listing of Analysis Population
- 13.6 Listing of Demographics
- 13.7 Listing of Medical and Surgical History
- 13.8 Listing of Prior and Concomitant Medication
- 13.9 Listing of Concomitant Anti-hypertension Medication
- 13.10 Listing of Study Drug Administration
- 13.11 Listing of Patients Receiving Various Batches of Investigational Products
- 13.12 Listing of 24-Hour Mean ABPM
- 13.13 Listing of Individual Office Sitting BP Readings
- 13.14 Listing of Average Office BP
- 13.15 Listing of Individual HBPM Readings
- 13.16 Listing of Weekly Average of HBPM
- 13.17 Listing of Serum AGT
- 13.18 Listing of RAS Biomarkers
- 13.19 Listing of Adverse Events
- 13.20 Listing of Serious Adverse Events
- 13.21 Listing of Adverse Events of Clinical Interest
- 13.22 Listing of Adverse Events of Hepatic including AEs of LFT abnormalities
- 13.23 Listing of Adverse Events of Hyperkalemia
- 13.24 Listing of Adverse Events of Hypotension and Potential Hypotension
- 13.25 Listing of Adverse Events of Acute Renal Failure

- 13.26 Listing of Injection Site Reactions
- 13.27 Listing of Deaths
- 13.28 Listing of Vital Signs, Weight, Height and BMI
- 13.29 Listing of Pregnancy Test
- 13.30 Listing of Physical examination
- 13.31 Listing of 12-lead Electrocardiogram
- 13.32 Listing of 24-hour Holter Electrocardiogram
- 13.33 Listing of Hematology
- 13.34 Listing of Serum Chemistry
- 13.35 Listing of Liver Function Tests
- 13.36 Listing of Coagulation
- 13.37 Listing of Urinalysis
- 13.38 Listing of Laboratory Abnormalities
- 13.39 Listing of Liver Function Test Results for Patients with Abnormal LFT
- 13.40 Listing of Serum Chemistry Potassium Results for Patients with Post Baseline >5.5 (mmol/L)
- 13.41 Listing of Patients with 30% eGFR reduction from Baseline
- 13.42 Listing of Normal Ranges for Laboratory Parameters
- 13.43 Listing of Anti-drug Antibodies Test Results
- 13.44 Listing of individual Plasma Zilebesiran Pharmacokinetic Concentrations
- 13.45 Listing of individual Urine Zilebesiran Pharmacokinetic Concentrations
- 13.46 Listing of individual Plasma Zilebesiran Pharmacokinetic Parameters
- 13.47 Listing of individual Urine Zilebesiran Pharmacokinetic Parameters

14. Citations

Not applicable.

Appendix 1: Software, Dictionary

The following software and versions will be used.

	Software and Versions
OS	Microsoft Windows 10
Statistical analysis software	SAS 9.4 or later
Tabulation software	Microsoft Word 2016
WHO-Drug Dictionary	Version Global C3 Mar 2022
MedDRA	Version 25.0

Appendix 2: The list of Unit and Display digit for quantitative item

Assessment Classification	Item name	Unit	Display digit
Efficacy ABPM, OBP, HBPM			
	Systolic blood pressure	[mmHg]	1
	Diastolic blood pressure	[mmHg]	1
Pharmacodynamic (PD)			
	Serum AGT	[ng/mL]	1
Biomarker Evaluation			
	Plasma renin concentration	[ng/mL]	
	Plasma renin activity	NA	1
	Aldosterone/Renin Activity	NA	1
	Aldosterone serum	NA	1
Pharmacokinetics Concentrations			
	Plasma zilebesiran concentrations	[ng/mL]	1
	Urine zilebesiran concentrations	[ng/mL]	1
	Metabolite plasma AS(N-1)3' zilebesiran concentration	[ng/mL]	1
	Metabolite urine AS(N-1)3' zilebesiran concentration	[ng/mL]	1
Pharmacokinetics parameters, Metabolite	AUC ₀₋₂₄	[ng*h/mL]	3 significant figures
	AUC _{0-last}	[ng*h/mL]	3 significant figures
	AUC _{0-inf}	[ng*h/mL]	3 significant figures
	AUC _{%extrap}	[%]	3 significant figures
	C _{max}	[ng/mL]	3 significant figures
	T _{max}	[h]	3 significant figures
	T _{1/2}	[h]	3 significant figures
	CL/F	[L/h]	3 significant figures
	V _z /F	[L]	3 significant figures
	λ _z	[1/h]	3 significant figures
Pooled urine Pharmacokinetic Parameters, Metabolite Urine	MRCMAX	NA	3 significant figures
	MRAUC	NA	3 significant figures
	Ae	[mg]	3 significant figures
	fe	[%]	3 significant figures
	CL _R	[L/h]	3 significant figures
Safety Vital sign			
	Height	[cm]	0.1
	Weight	[kg]	0.1
	BMI	[kg/m ²]	0.1
	Body Temperature	[°C]	0.1

Assessment Classification	Item name	Unit	Display digit
ECG	Heart Rate	[beats/min]	1
	Respiratory Rate	[beats/min]	1
	ECG Ventricular rate	[beats/min]	1
	RR Interval	[msec]	1
	PR Interval	[msec]	1
	QRS Duration	[msec]	1
	QT Interval	[msec]	1
	QTcF Interval	[msec]	1
	ECG Mean Heart Rate	[beats/min]	1
	QTcB Interval	[msec]	1
Laboratory test Hematology			
	Basophils	[%]	0.1
	Basophils (Absolute Ct)	[10 ⁹ /L]	0.01
	Nucleated Red Blood Cell, % (Sysmex)	[%]	0.1
	Eosinophils	[%]	0.1
	Eosinophils (Absolute Ct)	[10 ⁹ /L]	0.01
	Immature Granulocytes	[%]	0.1
	Immature Granulocytes/Leukocytes	[10 ⁹ /L]	0.01
	Hematocrit	[%]	0.1
	Hemoglobin	[g/L]	0.1
Serum Chemistry	Platelets	[×10 ⁴ /μL]	0.1
	Lymphocytes	[%]	1
	Lymphocytes/Leukocytes	10 ⁹ /L	0.01
	Ery. Mean Corpuscular Hemoglobin	[pg]	0.1
	Ery. Mean Corpuscular HGB Concentration	[g/dL]	0.1
	Ery. Mean Corpuscular Volume	[fL]	0.1
	Monocytes	[%]	0.1
	Monocytes/Leukocytes	[10 ⁹ /L]	0.01
	Mean Platelet Volume	[fL]	0.1
	Neutrophil	[%]	0.1
	Neutrophils/Leukocytes	[10 ⁹ /L]	0.01
	Erythrocytes	[10 ¹² /L]	0.01
	Nucleated Erythrocytes	[10 ⁹ /L]	0.01
	Erythrocytes Distribution Width	[%]	0.1
	Leukocytes	[10 ⁹ /L]	0.01
	Sodium	[mmol/L]	1
	Triglycerides	[mg/dL]	1
	Urea Nitrogen	[mg/dL]	1
	Urate	[mg/dL]	0.1
	Protein	[g/dL]	0.1
	Glucose	[mmol/L]	1
	Creatinine	[mg/dL]	0.1
	eGFR	[mL/min/1.73 m ²]	1

Assessment Classification	Item name	Unit	Display digit
Liver Function Tests	Choriogonadotropin Beta	[IU/L]	0.1
	Potassium	[mmol/L]	0.1
	Phosphate	[mmol/L]	0.1
	Albumin	[g/L]	0.01
	Calcium	[mmol/L]	0.1
	Bicarbonate	[mEq/L]	1
	Chloride	[mEq/L]	1
	AST	[U/L]	1
	ALT	[U/L]	1
	GGT	[U/L]	1
	ALP	[U/L]	1
	Direct Bilirubin	[mg/dL]	0.01
	Total Bilirubin	[mg/dL]	0.01
Urinalysis	pH	[pH]	1
	Specific gravity	NA	0.001
	Bacteria	[/HPF]	1
	Color	NA	1
	Granular Casts	[/LPF]	1
	Hyaline Casts	[/LPF]	1
	RBC Casts	[/LPF]	1
	Waxy Casts	[/LPF]	1
	WBC Casts	[/LPF]	1
	Amorphous Crystals	[/HPF]	1
	Calcium Carbonate Crystals	[/HPF]	1
	Calcium Oxalate Crystals	[/HPF]	1
	Calcium Phosphate Crystals	[/HPF]	1
	Cystine Crystals	[/HPF]	1
	Leucine Crystals	[/HPF]	1
	Triple Phosphate Crystals	[/HPF]	1
	Tyrosine Crystals	[/HPF]	1
	Uric Acid Crystals	[/HPF]	1
	Renal Epithelial Cells	[/HPF]	1
	Squamous Epithelial Cells	[/HPF]	1
	Transitional Epithelial Cells	[/HPF]	1
	Ketones	[mg/dL]	1
	Albumin	NA	1
	Urinary Glucose	[mg/dL]	1
	Urinary protein	[mg/dL]	1
	Nitrite	NA	1
	Leukocytes Esterase	NA	1
	Erythrocytes	[/HPF]	1
	Specimen Appearance	NA	1
	Urinary Blood	NA	1
	Urinary Mucus	NA	1
	Urobilinogen	[mg/dL]	1
	Leukocytes	[/HPF]	1

Assessment Classification	Item name	Unit	Display digit
Coagulation	Yeast Cells	NA	1
	Activated Partial Thromboplastin Time	[s]	0.1
	Prothrombin Time	[s]	0.1
	Prothrombin Time - INR	NA	0.1
Glycemic Assessment	Hemoglobin A1C	[%]	0.1
FSH	Follicle Stimulating Hormone	[IU/L]	0.1

Appendix 3: The list of AE terms for Hyperkalemia and Potentially related to hypotension

AE type	AE Preferred Terms
Hyperkalemia	Hyperkalemia
	Blood potassium increased
	Blood potassium abnormal

AE type	AE Preferred Terms	Final Classification
Potential Hypotension	Arterial pressure NOS decreased	Narrow (FMQ)
	Blood pressure decreased	Narrow (FMQ)
	Blood pressure diastolic decreased	Narrow (FMQ)
	Blood pressure systolic decreased	Narrow (FMQ)
	Diastolic hypotension	Narrow (FMQ)
	Hypotension	Narrow (FMQ)
	Hypotension aggravated	Narrow (FMQ)
	Hypotension NOS	Narrow (FMQ)
	Hypotension on induction	Narrow (FMQ)
	Hypotension postural aggravated	Narrow (FMQ)
	Hypotensive anaesthesia procedure	Narrow (FMQ)
	Hypotensive transfusion reaction	Narrow (FMQ)
	Intraoperative hypotension	Narrow (FMQ)
	Neonatal hypotension	Narrow (FMQ)
	Orthostatic hypotension	Narrow (FMQ)
	Postoperative hypotension	Narrow (FMQ)
	Postural hypotension	Narrow (FMQ)
	Procedural hypotension	Narrow (FMQ)
	Blood pressure abnormal	Broad (FMQ)
	Blood pressure ambulatory abnormal	Broad (FMQ)
	Blood pressure ambulatory decreased	Broad (FMQ)
	Blood pressure diastolic abnormal	Broad (FMQ)
	Blood pressure orthostatic abnormal	Broad (FMQ)
	Blood pressure orthostatic decreased	Broad (FMQ)
	Blood pressure systolic abnormal	Broad (FMQ)
	Blood pressure systolic inspiratory decreased	Broad (FMQ)
	Dehydration	Broad (FMQ)
	Haemorrhagic adrenal infarction	Broad (FMQ)
	Hypovolaemia	Broad (FMQ)
	Procedural shock	Broad (FMQ)
	Orthostatic intolerance	Additional
	Dizziness	Additional
	Dizziness exertional	Additional
	Dizziness postural	Additional
	Presyncope	Additional
	Syncope	Additional
	Hypotensive crisis	Additional
	Mean arterial pressure decreased	Additional

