5.7. Monitoring for Potential Clinical Events

5.7.1. Monitoring and Approach for Potential Hypotension

Hypotension is an obligate risk of antihypertensive medications. In addition to office blood pressure monitoring, outpatient blood pressure will be monitored weekly with HBPM to ensure the early detection of potential hypotension. Whenever possible, management decisions will be based on blood pressure measurements confirmed by office blood pressure.

The following management recommendations for hypotension are provided:

- Patients who experience low blood pressure that is associated with symptoms should promptly seek medical evaluation at the clinical study site or another hospital setting. Clinical study site evaluation for low blood pressure should include the assessment of orthostatic blood pressure (seated to standing).
- The Investigator should consider downtitration or interruption of oral antihypertensives (if taking) if confirmed office SBP <90 mmHg or if clinical symptoms, such as lightheadedness or dizziness, develop coupled with a significantly lower SBP compared to prior visits (ie, SBP <100 mmHg).
- Clinically significant events discovered during the course of a patient's general medical care should be promptly communicated to the site and evaluated by the Investigator, especially if hypotension is noted. Patients will carry Institutional Review Board (IRB)/Independent Ethics Committee (IEC)-approved patient cards to facilitate this physician-to-physician communication.
- If hypotension is confirmed, serum electrolytes and creatinine should be measured and any oral antihypertensive(s) should be downtitrated or interrupted per Investigator judgement as outlined above.
- The frequency of blood pressure and laboratory monitoring (serum electrolytes and creatinine) should be increased during intercurrent illnesses that predispose patients to dehydration (eg, vomiting or diarrhea that persists for more than 24 hours) or when symptoms consistent with decreased effective circulating volume (eg, presyncopal symptoms, unexplained falls, decreased urine output) manifest, even if a patient's recent blood pressure measurements have been normal.

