- Hypotension that warrants direct evaluation at the site should be communicated to the Medical Monitor within 24 hours. In addition, other clinical events consistent with potential hypotension (eg, unexplained presyncope, syncope, or falls) should be communicated to the Medical Monitor within 24 hours of the site being notified.
- Management of persistent hypotension may include increased salt intake or, if unresponsive, standard treatments for hypotension, such as fludrocortisone or midodrine.
- Low blood pressure that requires medical treatment (including intravenous fluid support) or other clinical events consistent with potential hypotension (see above) should be recorded as AEs.

Clinical signs/symptoms consistent with hypotension, including but not limited to lightheadedness, dizziness, and syncope, coupled with a significantly lower SBP compared to prior visits, or any significantly lower SBP compared to prior visits that requires clinical intervention must be recorded as an AE of clinical interest (Section 6.5.6.1).

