Adverse Events of Clinical Interest	
The following are considered to be AEs of clinical interest:
 
 • ALT or AST >3×ULN. • Severe or serious ISRs 
An ISR is defined as a local reaction at or near the site of injection. “At or near” the injection site includes reactions at the injection site, adjacent to the injection site, or a reaction which may shift slightly away from the injection site due to gravity (eg, as may occur with swelling or hematoma). A systemic reaction which includes the injection site, eg, generalized urticaria, other distinct entities or conditions like lymphadenopathy that may be near the injection site is not considered an ISR.
 
 • Hyperkalemia, defined as any potassium elevation >5.5 mmol/L that has been confirmed by a second measurement (serum or plasma) or that requires clinical intervention. • Hypotension, defined as – clinical signs/symptoms consistent with hypotension, including but not limited to lightheadedness, dizziness, and syncope, coupled with a significantly lower SBP compared to prior visits,

Item name	Definitions						
	
OR – any significantly lower SBP compared to prior visits that requires clinical intervention.
 
 Clinically significant renal function decline, defined as a decrease in eGFR by $\geq 30\%$ from baseline and to eGFR < 60 mL/min/1.73m². 						

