3.3 Handling of Safety Data

3.3.1 Handling of Adverse Events

Adverse events will be coded according to the Medical Dictionary for Regulatory Activities and summarized by System Organ Class (SOC) and PT by dose level and overall. AEs, SAEs, study-drug related AEs, AEs leading to withdrawal from study, and AEs leading to death will be summarized by SOC and PT for each treatment arm and overall. Additionally Hepatic AEs, including AEs of LFT abnormalities, Hyperkalemia, Hypotension, Potential Hypotension and Acute renal failure will be summarized by SOC and PT for each treatment arm and overall. AEs, SAEs, and study-drug related AEs will be summarized by PT for each treatment arm and overall. By-patient listings will also be provided.

1) For summary tables

Treatment-emergent Adverse Event from throughout the double-blind treatment period will be included.

- First study drug administration date Onset date of Adverse Events \leq first study drug administration + 169 days.
- Treatment related AEs that occur after 169 days of first study drug administration are also counted as TEAE.

AEs with Missing or partial dates will be handled per section 3.1.1.

An AE with missing severity will be assumed to be severe.

An AE with missing study drug relatedness will be assumed to be related.

2) For listings

All Adverse Events from screening period through safety-follow up period will be included.

Missing study drug relatedness and missing severity will be presented as collected in the EDC.

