12.1.2 Summary of Treatment-emergent Adverse Events by SOC and PT

Target population	:	Safety Analysis Set
Analysis Items	:	
 • Treatment-emergent Adverse Events • Study Drug Related Treatment-emergent Adverse Events • Treatment-emergent Serious Adverse Events • Study Drug Related Treatment-emergent Serious Adverse Events • Treatment-emergent Adverse Events leading to withdrawal from study • Treatment-emergent Adverse Events leading to death • Hepatic Treatment-emergent Adverse Events including AEs of LFT abnormalities • Treatment-emergent Adverse Events of Hyperkalemia • Treatment-emergent Adverse Events of Hypotension and Potential Hypotension • Treatment-emergent Adverse Events of Acute Renal Failure
Group	:	Placebo, Zilebesiran 300 mg, Zilebesiran 600 mg, Total zilebesiran, Overall Total
Content of analysis	:	
 • The number of patients with the event and the percentage, the number of events will be calculated for each group.
Definitions	:	
 • The denominator of proportions is the target population by groups. • Hepatic AEs, including AEs of Liver Function Test (LFT) abnormalities (SMQ all narrow and broad terms) • Hyperkalemia (CMQ) (Refer to Appendix 3) • Hypotension (FMQ narrow terms) • Potential Hypotension (Refer to Appendix 3) • Acute renal failure (SMQ all narrow and broad terms)

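### SAP Appendix 3 has no fall term, although Protocol 5.7.1 gives unexplained falls as an example of potential hypotension, so the grouped hypotension table can miss a patient whose only event is such a fall

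*SAP*

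**What the plan says.** Protocol 5.7.1 mentions falls twice. One bullet says that "other clinical events consistent with potential hypotension (eg, unexplained presyncope, syncope, or falls) should be communicated to the Medical Monitor", and a later bullet adds that "other clinical events consistent with potential hypotension (see above) should be recorded as AEs". Before that, in the advice on closer monitoring, the section speaks of "symptoms consistent with decreased effective circulating volume (eg, presyncopal symptoms, unexplained falls, decreased urine output".

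SAP 12.1.2 plans a table by arm of "Treatment-emergent Adverse Events of Hypotension and Potential Hypotension". Hypotension is selected there by FMQ narrow terms. The other component is given only as "Potential Hypotension (Refer to Appendix 3".

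Appendix 3, titled "The list of AE terms for Hyperkalemia and Potentially related to hypotension", is a closed list of preferred terms. Its potential-hypotension terms fall in three classes: narrow FMQ, broad FMQ and Additional. Presyncope and Syncope are in the Additional class. No term in any class refers to a fall, and the SAP does not comment on this. Section 13 of the SAP gives only a title for listing 13.24, which covers the same two categories, so I assume that it uses the same selection.

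**The concern.** The protocol gives three examples of clinical events that may signal low blood pressure. The SAP's list carries two of them. A patient who has an unexplained fall, with nothing else on the list reported, fits the protocol's description of potential hypotension but would not be counted in the table meant to show that category by arm.

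Safety is the primary objective, and Protocol 1.3.2 names hypotension among the possible risks. With 12 patients per arm the grouped count will be small, so one patient more or less changes how the row reads.

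The omission does not look like a deliberate choice of a more specific list. The sponsor added its own Additional class to the FMQ terms and put Presyncope and Syncope there. The protocol's qualifier (unexplained) stands before all three examples, yet the SAP counts presyncope and syncope without it. The list also accepts non-specific terms such as Dizziness and Dehydration.

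**Working it through.** The plan states no figure on this point, so there is none to reproduce. The check is a comparison of texts, followed by arithmetic for scale.

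**Step 1. Compare the protocol's examples with the SAP's list.** Appendix 3 has 18 narrow + 12 broad + 8 Additional = 38 potential-hypotension terms.

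| Example in Protocol 5.7.1 | Term in SAP Appendix 3 |
|---|---|
| Presyncope | Yes (Additional) |
| Syncope | Yes (Additional) |
| Falls | None of the 38 |

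**Step 2. See where a lone unexplained fall would appear.**

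- Grouped hypotension table (SAP 12.1.2): no.
- Listing 13.24: no, if it uses the same terms.
- General tables by SOC and PT (12.1.2) and by PT (12.1.4): yes, if treatment-emergent.
- Table of most common events (12.1.6): yes, if treatment-emergent. Its threshold is 5% in any arm, and one patient in 12 is 8.3%.
- AE listing (13.19): yes. SAP 3.3.1 says of listings that "All Adverse Events from screening period through safety-follow up period will be included".
- Listing of AEs of clinical interest (13.21): only if the definition in SAP 2.5.1 is met. Its first limb needs "clinical signs/symptoms consistent with hypotension, including but not limited to lightheadedness, dizziness, and syncope, coupled with a significantly lower SBP" compared with prior visits. Its second limb needs a significantly lower SBP that requires intervention. A fall at home with no blood pressure reading may meet neither.

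**Step 3. Weight of one patient.** With 12 patients per arm (Protocol 7.1):

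- one arm: 1/12 = 8.3 percentage points
- pooled zilebesiran: 1/24 = 4.2 percentage points

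**Step 4. Compare with the expected count.** Protocol 1.2 reports at least one potential-hypotension AE in 7.9% of zilebesiran patients in Study 002. Applying that rate here, which is an assumption because that study's term list is not given:

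- per zilebesiran arm: 12 × 0.079 = 0.95 patients; chance of at least one = 1 − 0.921^12 = 63%
- pooled zilebesiran: 24 × 0.079 = 1.9 patients; chance of at least one = 1 − 0.921^24 = 86%

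One missed patient would be large against a count of about two.

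**Step 5. How many might be missed.** Let p be the risk, over the double-blind period, that a patient has an unexplained fall and no other listed term. The documents do not give p, so the values below are assumptions. Among 24 zilebesiran patients, the expected number missed is 24p and the chance of missing at least one is 1 − (1 − p)^24.

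| Assumed p | Expected number missed | Chance of at least one |
|---|---|---|
| 1% | 0.24 | 21% |
| 2% | 0.48 | 38% |
| 5% | 1.2 | 71% |

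These rows show only what each assumed p implies. They are not a forecast.

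**The case against.** The strongest case for leaving the list alone has four parts.

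- **The protocol passage is not a case definition.** It introduces its list with eg, in a bullet about what to communicate to the Medical Monitor. The formal definition of hypotension as an AE of clinical interest (Protocol 6.5.6.1, SAP 2.5.1) names lightheadedness, dizziness and syncope, not falls. This stands. A reader might infer that the SAP breaks a protocol definition, and the documents do not support that.
- **A patient is missed only under two conditions.** The fall must be unexplained, and no listed term such as Dizziness, Presyncope, Syncope or Orthostatic hypotension may be reported with it. This stands too. A reader might infer that the table will under-count. The documents support only that it can.
- **The event is not lost.** As Step 2 shows, a treatment-emergent fall appears by arm in the general tables, and low pressure is tabulated directly in SAP 12.2.2 and 12.2.3. The primary endpoint is unaffected, and the analyses are descriptive (Protocol 7.2). This stands, but none of those outputs links the fall to hypotension, which is the purpose of the grouped table. The blood pressure summaries rest on readings taken at visits.
- **A bare fall term brings in mechanical falls.** The protocol means unexplained falls. Each mechanical fall would add the same 8.3 points to an arm, and a row with and without *Fall* shows only the effect of all falls together. This stands, and it is why the added term needs a case review beside it.

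It might also be said that the existing list keeps the row comparable with earlier studies. The documents do not say which list those studies used, so that argument has no support here.

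**Conclusion.** This is a minor mismatch between protocol and SAP. The SAP carries two of the protocol's three examples and does not explain the absence of the third. The consequence is conditional: the grouped table can miss a patient whose only reported event is an unexplained fall, and the same holds for listing 13.24 if it uses the Appendix 3 terms. Each such patient is worth 8.3 points in an arm or 4.2 points in the pooled zilebesiran group. The documents do not say how many there will be, and zero is possible. The percentages assume full enrolment of 12 per arm with all patients dosed. The conclusion affects only how AEs are grouped for display.

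**What to change.** Before any analysis by arm:

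1. Add *Fall* to the Additional class of Appendix 3 (38 terms become 39), checking the wording against the dictionary version in SAP Appendix 1.
2. In SAP 12.1.2, show the potential-hypotension row with and without *Fall*.
3. Have each reported fall classed as explained or unexplained by reviewers who do not know the arm, and flag the unexplained ones in listing 13.24. Protocol 3.5 says that the sponsor is unblinded to assignment, so the reviewers must come from staff who remain blinded.
4. Record the change and its reason in the SAP revision history, as SAP 1.1 requires. Adding the term after falls have been seen by arm would look data-driven.

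If the sponsor prefers to leave falls out, a sentence in Appendix 3 giving the reason is the minimum.

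The cost is one term, one extra row and a little review work. The downside is that mechanical falls may enter the wider row. The narrower row and the classification of each fall keep that visible.
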